#### **6.4.3. Analysis for the Secondary and Exploratory Immunogenicity Objectives**

Part A and B:

Immunogenicity, including the SARS-CoV-2-specific bAb and nAb along with seroresponse rate, will be assessed at multiple time points in this study (Days 1, 15, 29, 91, 181 and 366); however, Day 29, 28 days after booster dose, is the time point of primary interest.

The following evaluations will be performed at each time point for immunogenicity.

- In relation to the immune response of each booster arm to SARS-CoV-2 prototype and viral variants, the GMT or level, GMFR and SRR will be calculated at the time points where the immune response is assessed for prototype and viral variants. For each antibody of interest, the GMT or level and GMFR with their corresponding 95% CIs at each time point will be provided. The 95% CIs will be calculated based on the t-distribution of the log-transformed values then back-transformed to the original scale for presentation. The following descriptive statistics will also be provided at each time point: number of participants (n), median, minimum, and

maximum. Additionally, reverse cumulative distribution plots and box plots of titers or levels will be generated for each antibody of interest.

- For each antibody of interest, the proportion of subjects with fold-rise  $\geq 2$ , fold-rise  $\geq 3$ , and fold-rise  $\geq 4$  from baseline at each post-injection time point will be tabulated with its 95% CI calculated using the Clopper-Pearson method.
- The SRR of each treatment group against the prototype strain and variant strains, defined as the percentage of participants achieving seroresponse against the prototype strain and variant strains, respectively, will be provided with their 95% CI calculated with the Clopper-Pearson method.
- For the exploratory objectives, to characterize cellular immunogenicity, frequency, magnitude, and phenotype of antigen-specific B- and T-cells may be analyzed; comparison of the SARS-CoV-2 genetic sequence of viral isolates with the vaccine sequence and immune responses to vaccine breakthrough isolates may be performed to evaluate the genetic and/or phenotypic relationships of isolated SARS-CoV-2 strains to the vaccine sequence.

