#### **3.1.2. Secondary Endpoints**

The secondary objective will be evaluated by the following endpoints:

Immune response of the mRNA-1283 and mRNA-1283.211 vaccines against the ancestral SARS-CoV-2 and SARS-CoV-2 variants, including B.1.351 and B.1.1.529, at all immunogenicity time points (Days 1, 15, 29, 91, 181 and 366) by GMT, GMFR, and SRR.

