### **3.2.2. Secondary Endpoints**

The secondary objective will be evaluated by the following endpoints:

Immune response of the mRNA-1283.529 vaccine by dose level against the ancestral SARS-CoV-2 and SARS-CoV-2 variants, including B.1.529, at all immunogenicity time points (Days 1, 15, 29, 91, 181 and 366) by GMT, GMFR, and SRR.

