### **5.4. Per-Protocol (PP) Immunogenicity Set (PPIS)**

The PPIS consists of all participants in the FAS who receive the planned dose of IP, have pre-booster and Day 29 neutralizing antibody data against prototype virus strain, have no previous HIV infection and who have no major protocol deviations that impact key or critical data. Participants will be included in the treatment group to which they were randomized/enrolled. The PPIS will be used as the sensitivity analysis set for analyses of immunogenicity.

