### **5.5. Per-Protocol Immunogenicity Set – Pre-booster SARS-CoV-2 Negative (PPIS-Neg)**

The PPIS-Neg consists of participants who are in PPIS and are pre-booster SARS-CoV-2 negative, defined as no virologic or serologic evidence of SARS-CoV-2 infection on or before booster, i.e., RT-PCR result is not positive if available at pre-booster and a negative bAb specific to SARS-CoV-2 nucleocapsid on or before booster. The PPIS-Neg will be used as the analysis set for the primary analyses of immunogenicity.

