### 6.4. Immunogenicity Analysis

The analyses of immunogenicity will be based on the PPIS and PPIS-Neg and will be performed by treatment group as defined in [Section 6.1](#).

The geometric mean titer (GMT) and geometric mean (GM) level will be calculated using the following formula:

$$10^{\left\{ \frac{\sum_{i=1}^n \log_{10}(t_i)}{n} \right\}}$$

where  $t_1, t_2, \dots, t_n$  are  $n$  observed immunogenicity titers or levels.

The geometric mean fold-rise (GMFR) measures the changes in immunogenicity titers or levels within subjects. It will be calculated using the following formula:

$$10^{\left\{ \frac{\sum_{i=1}^n \log_{10}\left(\frac{v_{ij}}{v_{ik}}\right)}{n} \right\}} = 10^{\left\{ \frac{\sum_{i=1}^n \log_{10}(v_{ij}) - \log_{10}(v_{ik})}{n} \right\}}$$

where, for  $n$  subjects,  $v_{ij}$  and  $v_{ik}$  are observed immunogenicity titers or levels for subject  $i$  at time points  $j$  and  $k$ ,  $j \neq k$

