#### 6.4.2. Analysis for the Primary Immunogenicity Objective

For Part A and Part B, PPIS-Neg will be used as primary analysis set. Sensitivity analyses may be performed using PPIS and a subset of PPIS-Neg only including subjects with no virologic or serologic evidence of SARS-CoV-2 infection on or before Day 29 or Day 91, i.e., RT-PCR results are not positive up to Day 29 or Day 91 and negative bAb specific to SARS-CoV-2 nucleocapsid on or before Day 29 or Day 91. The comparison of immunogenicity between the different vaccines is descriptive.

Part A:

For the primary immunogenicity endpoints of levels of serum nAb and bAb against SARS-CoV-2 prototype virus strain and its variant strains including B.1.351, immune response of each treatment group will be assessed with respect to mRNA-1273 CCI booster dose.

An analysis of covariance (ANCOVA) model will be employed to compare immune response of each treatment group with that of mRNA-1273 CCI booster dose. Day 29 serum bAb or nAb (against prototype virus strain or the variant strain) will be included in the model as a dependent variable and a treatment group variable (mRNA-1283 at each dose level, mRNA-1283.211 at each dose level, and mRNA-1273 CCI) will be included

as the fixed effect. The model will also adjust for age group (18-55, and  $\geq$ 56 years of age) and the pre-booster baseline value.

The GMT or GM level will be estimated by the geometric least square mean (GLSM) from the model for each treatment group and its corresponding 95% CI will be provided.

The GMR (ratio of GMTs or GM levels) for each treatment group with respect to mRNA-1273 CCI booster dose will be estimated by the ratio of GLSM from the model. The 95% CI of the ratio of GLSM will be provided to assess the between-group difference (each treatment group against mRNA-1273 CCI booster dose) in immune response against the prototype strain (or variant strains).

The primary immunogenicity endpoints of Part A will also be assessed by the vaccine seroresponse against SARS-CoV-2 prototype virus strain and against variant strains including B.1.351. Vaccine seroresponse at a time point is defined by an increase of SARS-CoV-2 specific bAb level or nAb titer to at least 4xLLOQ if the baseline is below the lower limit of quantification (<LLOQ), or a 4-fold or greater rise if pre-booster  $\geq$  LLOQ.

Two types of baselines for Part A will be employed to compute the seroresponse:

- 1) Pre-vaccination (Pre-Dose 1 of the primary series)

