- 2) Pre-booster

Seroresponse based on pre-vaccination is defined as  $\geq$  4\*LLOQ for subjects with negative SARS-CoV-2 status at their pre-vaccination baseline. For this study, subjects SARS-CoV-2 status at pre-booster baseline will be used to impute their SARS-CoV-2 status pre-vaccination baseline. If the participant tests negative at pre-booster, the serum Ab value of the pre-vaccination baseline will be imputed with LLOQ, otherwise, For subjects with positive SARS-CoV-2 status at pre-booster, their seroresponse based on pre-vaccination baseline will be set to missing.

The SRR at Day 29 will be summarized for each treatment group with its 95% CI calculated with the Clopper-Pearson method. The difference of SRRs at Day 29 for mRNA-1283 at each dose level, mRNA-1283.211 at each dose level compared with mRNA-1273 will be provided with its 95% CI with the Miettinen-Nurminen method.

Part B:

Similar analysis methods will be used to analyze immunogenicity data for Part B. An ANCOVA model will be used to compare immune response between treatment group (██████████ mRNA-1283.529). Day 29 antibody titers against B.1.1.529 will be included in the model as a dependent variable and treatment group variable (mRNA-1283.529 at each dose level) will be included as fixed effect, adjusting for age group (< 56,  $\geq$  56) and the pre-booster baseline Ab value. The GMT will be estimated by the GLSM from the model for each group and corresponding 95% CI will be provided. The ratio of GMTs for CCI mRNA-1283.529 with respect to CCI mRNA-1283.529 booster dose will be estimated by the ratio of GLSM from the model. The 95% CI for the ratio of GLSM will be provided to assess the between-group difference in immune response against B.1.1.529.

SRR against B.1.1.529 at Day 29 will be summarized for each mRNA-1283.529 dose level with its 95% CI calculated using the Clopper-Pearson method. The difference of SRRs at Day 29 between two dose levels will also be calculated with 95% CI using the Miettinen-Nurminen method.

For Part B, seroresponse will be based on both pre-vaccination and pre-booster baseline as well. The derivation rule is the same as described in Part A.

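### Late antibody summaries (SAP 6.4.3) include titres taken after post-booster infection or a later authorised COVID-19 vaccine; the optional infection-free subset ends at Day 91, leaving Days 181 and 366 without one

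*SAP*

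**What the plan says.** SAP 6.4.3 plans GMT or level, GMFR, the proportions with at least 2-, 3- and 4-fold rise, and SRR. It states that immunogenicity "will be assessed at multiple time points in this study (Days 1, 15, 29, 91, 181 and 366"), with Day 29 of primary interest. The secondary endpoints attribute these results to the vaccines: "Immune response of the mRNA-1283 and mRNA-1283.211 vaccines against the ancestral" strain and variants in Part A (SAP 3.1.2), and "Immune response of the mRNA-1283.529 vaccine by dose level against the ancestral" strain and variants in Part B (SAP 3.2.2).

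The population is set in SAP 6.4: "The analyses of immunogenicity will be based on the PPIS and PPIS-Neg".
- PPIS (SAP 5.4) requires that participants "have pre-booster and Day 29 neutralizing antibody data against prototype virus strain", received the planned dose, had no previous HIV infection and had no major deviation affecting key data. It has no SARS-CoV-2 infection criterion.
- PPIS-Neg (SAP 5.5) adds "no virologic or serologic evidence of SARS-CoV-2 infection on or before booster".

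The one later infection rule is in SAP 6.4.2. It is a sensitivity subset of PPIS-Neg with "no virologic or serologic evidence of SARS-CoV-2 infection on or before Day 29 or Day 91". It is permitted rather than required, and it sits under the primary objective.

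For outside products, protocol 5.5.3 lists what may affect a participant's per-protocol evaluability. Authorised or licensed vaccines count from 28 days before to 28 days after the dose. Investigational or nonregistered products count throughout the study. SAP 6.2.6 defers the major-deviation rules until before database lock.

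**The concern.** Protocol 3.2 expects SARS-CoV-2 to circulate during the study. It notes that swabs and serology may help to separate infection from vaccine response. Under protocol 7.3.6, participants with confirmed COVID-19 continue all scheduled assessments, so titres after infection will be in the data. The SAP applies the separation, optionally, up to Day 91. It stops before Days 181 and 366, where exposure has had longest to accumulate.

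An authorised COVID-19 vaccine given more than 28 days after the dose meets no stated rule at any late visit. A reader of the late tables could then take mixed immunity for persistence of the study vaccine's response. If no rule is written in advance, any later attempt to separate the two will be post hoc.

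**Working it through.** **Text check.** Could any planned rule act on a late titre after an event?

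| Source | Acts on late post-event titres? |
|---|---|
| SAP 5.4, 5.5 (sets) | No: no infection criterion beyond the booster |
| SAP 6.4.2 subset | Infection only, optional, to Day 91 |
| SAP 6.1 (missing data) | No: missing results are not imputed, but post-event titres are not set to missing |
| SAP 6.5 (subgroup) | No: pre-booster status only |
| SAP 6.6 (infections) | Counts cases by arm; no link to titres |
| SAP 6.2.4 | Summarises non-study vaccination; no link to titres |
| Protocol 5.5.3 | Discretionary and per participant; authorised or licensed vaccines to 28 days only |
| SAP 6.2.6 | Deferred; no such exclusion stated |

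Infection data do exist at the late visits. SAP 4.1 plans anti-nucleocapsid serology and RT-PCR at Days 91, 181 and 366, and SAP 6.6.1.1 derives an infection date.

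**Size.** The plan has no figure to reproduce. It gives no infection rate, outside-vaccination rate or titre SD, so every input below is assumed: p = share of samples affected, b = fold rise caused by the event (2 to 10), log10 SD 0.4 to 0.5, titres lognormal.

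*GMT and GMFR.* The inflation factor is b^p.

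| p | b = 2 | b = 5 | b = 10 |
|---|---|---|---|
| 10% | 1.07 | 1.17 | 1.26 |
| 30% | 1.23 | 1.62 | 2.00 |
| 50% | 1.41 | 2.24 | 3.16 |

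*SRR, pre-booster baseline (4-fold rise).* With g the event-free late GMFR, the increase is p × [Φ(log10(gb/4)/SD) − Φ(log10(g/4)/SD)]. At p = 30%:
- g = 2 or 3: 6.8 to 22.0 points. The top value is g = 2, SD 0.4, b = 10: 0.3 × (96.0 − 22.6) = 22.0.
- g = 10: 3.6 to 6.3 points. The low value is SD 0.4, b = 2: 0.3 × (96.0 − 84.0) = 3.6.

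The rate is most sensitive when g lies just below the 4-fold cut-off, so the full range for g = 2 to 10 is 3.6 to 22.0.

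*SRR, pre-vaccination baseline.* SAP 6.4.2 reads "Seroresponse based on pre-vaccination is defined as" at least 4×LLOQ, for participants negative at that baseline. With m the event-free late GMT divided by 4×LLOQ, the increase is p × [Φ(log10(mb)/SD) − Φ(log10(m)/SD)]. At p = 30%:
- m = 1: 6.8 to 14.8 points
- m = 3: 2.7 to 5.1 points
- m = 10: 0.2 to 0.7 points

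**What censoring costs.** The one-arm GMT 95% CI factor is 10^(t × SD/√n). At SD 0.5:
- n = 70: 10^(1.995 × 0.5/√70) = 1.32
- n = 49 (30% lost): 10^(2.011 × 0.5/√49) = 1.39

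PPIS-Neg will start below 70 where previously infected participants enrol, which protocol 3.1 allows. From an assumed 50, going to 35 moves the factor from 1.39 to 1.49.

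Censoring can also bias upward. If affected participants would otherwise have had r-fold lower titres, the censored GMT is too high by r^p. At p = 30% this is 1.07 for r = 1.25 and 1.23 for r = 2. With r = b = 2, both summaries are 1.23 too high and agree exactly.

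**The case against.** The strongest reply is that a summary of observed titres, whatever happened after the dose, is a legitimate descriptive target. Nothing is formally tested, the sample size is descriptive, Day 29 is the time point of primary interest, and infections are tabulated by arm. This stands as a reason for low priority. It does not remove the mismatch between an unlabelled mixed summary and an endpoint worded as the vaccine's response.

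Several stronger readings are tempting, and the documents do not support them:
- *That every sample enters with no restriction.* Analyses are limited to PPIS and PPIS-Neg, and the deferred deviation rules could add exclusions.
- *That Day 91 has no infection rule.* The SAP 6.4.2 subset reaches it, though only as an option.
- *That outside products are ignored.* Protocol 5.5.3 covers licensed vaccines within 28 days and investigational or nonregistered products throughout.
- *That vaccinations after Day 29 are simply not captured.* Table 8 footnote 8 stops routine recording at 28 days, but other protocol and SAP text points to later data, so the position is unclear.
- *That arm comparisons or the Day 29 result are biased.* Nothing suggests unequal event rates between arms, and no modelled ratio is planned at Days 181 or 366.

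It is also fair to say that the calculated sizes are not evidence of actual bias, and that the censored summary is not a clean answer.

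**Conclusion.** The point holds in a limited form. For PPIS and PPIS-Neg participants, the late summaries include samples whether or not they follow a post-booster infection or an authorised COVID-19 vaccine given more than 28 days after the dose. For infection, no infection-free analysis is defined at Days 181 and 366, although the tests to build one are scheduled. The level attributed to the study vaccine can therefore be overstated.

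The size is illustrative only. It depends on the assumed share affected, fold rise and SD, and on where titres sit against the seroresponse cut-off. It runs from negligible (pre-vaccination SRR with titres still high) to a doubling of the GMT at 30% affected and a 10-fold rise. This is a cheap improvement to a secondary descriptive summary, of low priority.

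**What to change.** In SAP 6.4.3:

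1. Label the Day 91, 181 and 366 summaries as including titres after infection and after non-study COVID-19 vaccination.
2. Extend the SAP 6.4.2 infection-free analysis to Days 181 and 366 as a planned supportive summary in PPIS-Neg, covering GMT, GMFR, the fold-rise proportions and SRR on both baselines.
   - Set samples to missing from the first post-baseline positive RT-PCR or anti-nucleocapsid seroconversion, or from a recorded non-study COVID-19 vaccination.
   - Date the infection for every PPIS-Neg participant, without the 14-day start. The SAP 6.6.1.1 date cannot be used unchanged: it applies to participants negative under SAP 6.1, which needs a negative RT-PCR, while PPIS-Neg admits those with no baseline RT-PCR.
   - At Day 91, say whether this replaces the optional subset or how the two relate.
   - Report numbers and reasons by arm and visit.
3. Reconcile the passages on whether non-study vaccinations after Day 29 are recorded: Table 8 footnotes 6 and 8, protocol 5.5.2, 7.3.2 and 7.4.7, and the SAP's after-28-day period (6.1), medication summaries (6.2.4) and post category (Table 4).
4. State that the two summaries are a sensitivity pair and do not bracket the true value. Agreement between them does not show absence of bias.

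Items 1, 2 and 4 cost SAP wording and one table set, with no new visit or sample. Under item 3, any extension of recording would need a formal amendment with IRB approval (protocol 10.2.7) and possibly an eCRF change; the infection part does not depend on it. The downsides are wider late intervals and possibly informative censoring, which is why the summary should be supportive and not a replacement.

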## 6.5. Subgroup Analysis

Part A and B:

Selected immunogenicity and safety analyses will be assessed in the following subgroups:

- Age group (18-55, and  $\geq 56$  years of age)
- Pre-booster SARS-CoV-2 infection status (negative or positive)

## 6.6. Efficacy Analysis

Part A and B:

SARS-CoV-2 infection cases, including both symptomatic and asymptomatic cases, and COVID-19 cases, defined with both CDC and Moderna mRNA-1273 P301 study, by treatment group will be summarized.

Pre-booster SARS-CoV-2 status is described in [Section 6.1](#).

### 6.6.1. Endpoint Definition/Derivation

#### 6.6.1.1. Derivation of SARS-CoV-2 Infection

SARS-CoV-2 infection is considered as either positive status of COVID-19 or asymptomatic SAS-CoV-2 infection for participants with negative pre-booster SARS-CoV-

2 status. It will be counted starting 14 days after the dose of IP SARS-CoV-2 infection will be defined in participants with negative pre-booster SARS-CoV-2 status by either:

- bAb levels against SARS-CoV-2 nucleocapsid protein negative at Day 1 that becomes positive after the IP injection, OR
- Positive RT-PCR after the dose of IP.

The date of documented infection will be the earlier of:

- Date of positive post-baseline RT-PCR result, or
- Date of positive post-baseline serology test result

The time to the first SARS-CoV-2 infection will be calculated as:

Time to the first SARS-CoV-2 infection = Date of the first documented infection – Date of the IP injection + 1.

Cases will be counted starting 14 days after the IP injection. They will be summarized by treatment group.

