### **3.1.3. Exploratory Endpoints**

The exploratory objective will be evaluated by the following endpoints:

- Frequency, magnitude, and phenotype of antigen specific B- and T-cells, to include B-cell and T-cell receptor repertoires
- Laboratory-confirmed asymptomatic or symptomatic SARS-CoV-2 infection will be defined in participants:
  - Negative SARS-CoV-2 anti-nucleocapsid antibody blood test at Day 1 that becomes positive at Day 29 or later, OR
  - Positive SARS-CoV-2 reverse transcriptase polymerase chain reaction (RT-PCR) from nasopharyngeal swab
- Comparison of the SARS-CoV-2 genetic sequence of viral isolates with the vaccine sequence and characterization of immune responses to vaccine breakthrough isolates

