### 3.2.3. Exploratory Endpoints

The exploratory objective will be evaluated by the following endpoints:

- Frequency, magnitude, and phenotype of antigen-specific B- and T-cells, to include B-cell and T-cell receptor repertoires
- Laboratory-confirmed asymptomatic or symptomatic SARS-CoV-2 infection will be defined in participants:
  - Negative SARS-CoV-2 anti-nucleocapsid antibody blood test at Day 1 that becomes positive at Day 29 or later, OR
  - Positive SARS-CoV-2 RT-PCR from nasopharyngeal swab
- Comparison of the SARS-CoV-2 genetic sequence of viral isolates with the vaccine sequence and characterization of immune responses to vaccine breakthrough isolates

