## 4. Study Design

### 4.1. Overall Study Design

This is a Phase 2a study that consists of two parts: Part A is an observer-blind, stratified, randomized design to evaluate the immunogenicity, safety, and reactogenicity of mRNA-1283 and mRNA-1283.211 vaccines administered as a single booster dose to participants 18 years and older who were previously vaccinated with mRNA-1273, respectively. Part B is an open-label design to evaluate the immunogenicity, safety, and reactogenicity of mRNA-1283.529 administered as the second booster dose to participants 18 years and older who were previously vaccinated with mRNA-1273 primary series and a single mRNA-1273 booster dose (i.e., three doses of mRNA-1273).

Up to 420 participants in Part A who received the primary series of mRNA-1273 CCI with appropriate documentation at least 6 months prior will be randomized 1:1:1:1:1 (i.e., up to 70 participants per treatment group) to receive a single boost of mRNA-1283 at one of three dose levels CCI, a single boost of mRNA-1283.211 at one of two dose levels CCI, or a single dose of the active comparator, mRNA-1273 at a single dose level CCI (Table 1-1).

Up to 140 participants in Part B who received the primary series of mRNA-1273 CCI and a first booster dose of mRNA-1273 CCI at least 3 months prior will be enrolled in a 1:1 ratio (i.e., up to 70 participants per dose level) to receive a single boost of mRNA-1283.529 as the second booster dose at one of two dose levels CCI (Table 1-2).

Enrollment in both parts of this study will be stratified by age with two age strata: 18-55 years of age and  $\geq$ 56 years of age, with at least 20% but no more than 50% of participants 56 years of age or older. Those with documented prior SARS-CoV-2 infection are eligible to participate if also previously vaccinated with mRNA-1273. Prior infection status will be confirmed by anti-nucleocapsid antibody testing of all participants.

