#### 6.6.1.3. Derivation of COVID-19

The incidence of the first occurrence of symptomatic COVID-19 infection cases is recorded starting 14 days after the injection. Surveillance for COVID-19 will be conducted through monthly contact and scheduled blood collection. Subjects reporting COVID-19 symptoms will be arranged an illness visit to collect an NP swab.

Two definitions of the COVID-19 will be evaluated:

1. Primary case definition per the Phase 3 study (mRNA-1273-P301): Cases are defined as participants meeting clinical criteria based on both symptoms for the COVID-19 and positive RT-PCR test results as described in [Table 2-1](#).
2. Secondary case definition based on CDC criteria: The presence of one of the CDC-listed symptoms ([Table 2-2](#)) and a positive RT-PCR test on a respiratory sample.

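### SAP 6.6.1.1 and 6.6.1.2 require negative pre-booster status for RT-PCR-confirmed infection, a condition that the stated endpoint places on seroconversion only, while the denominator stays the whole FAS

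*SAP*

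**What the plan says.** **The endpoint.** SAP 3.1.3 (Part A) gives two limbs. The serology limb is "Negative SARS-CoV-2 anti-nucleocapsid antibody blood test at Day 1 that becomes positive at Day 29 or later, OR" and the other is "Positive SARS-CoV-2 reverse transcriptase polymerase chain reaction (RT-PCR) from nasopharyngeal swab". SAP 3.2.3 repeats this for Part B, with the second limb as "Positive SARS-CoV-2 RT-PCR from nasopharyngeal swab". Protocol Tables 1 and 2 carry the same two limbs. Protocol 7.3.6 and the protocol glossary define asymptomatic infection in the same pattern: RT-PCR without a baseline condition, or serology turning positive after a negative enrolment test.

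**The derivation.** SAP 6.6.1.1 opens with "SARS-CoV-2 infection is considered as either positive status of COVID-19 or asymptomatic SAS-CoV-2 infection for participants with negative pre-booster SARS-CoV" (the virus name and the word status run over a page break). It then gives the operative rule, "SARS-CoV-2 infection will be defined in participants with negative pre-booster SARS-CoV-2 status by either", followed by a seroconversion limb and the limb "Positive RT-PCR after the dose of IP". SAP 6.6.1.2 limits asymptomatic infection to the same pre-booster-negative participants.

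**COVID-19.** SAP 6.6.1.3 says "The incidence of the first occurrence of symptomatic COVID-19 infection cases is recorded starting 14 days after the injection". Neither of its two case definitions (Tables 2-1 and 2-2) refers to pre-booster status.

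**Who is analysed.** SAP 4.1 states "Those with documented prior SARS-CoV-2 infection are eligible to participate if also previously vaccinated with mRNA-1273". SAP 6.6.2 summarises these events on the FAS, which has no baseline-status restriction (SAP 5.3). SAP 6.1 makes the analysis set by arm the default denominator. SAP section 7 declares no departure from the protocol.

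**The concern.** The derivation does not implement the endpoint it serves. A participant who is anti-nucleocapsid positive and RT-PCR negative on Day 1, and who later has a positive study swab, meets the RT-PCR limb of the endpoint. SAP 6.6.1.1 gives that participant no infection. With symptoms, the same participant is a COVID-19 case under 6.6.1.3. Without symptoms, the event is in no summary under 6.6, although protocol 7.3.6 calls it asymptomatic infection.

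Previously infected people may enrol, so the situation will arise. At stake are the infection and asymptomatic-infection counts and percentages by arm. The numerator excludes people whom the denominator includes, and the infection and COVID-19 rows of one display would rest on different populations.

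**Working it through.** The plan gives no event rate, effect size or precision target for this endpoint, so there is no stated figure to reproduce. The check has two parts.

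**1. Definitions side by side.** Take a participant with a positive RT-PCR at least 14 days after injection, so that the counting window plays no part, and no seroconversion. Symptomatic means meeting a case definition in 6.6.1.3.

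| Pre-booster status | Symptoms | Endpoint (SAP 3.1.3/3.2.3) | Infection (6.6.1.1, operative rule) | Asymptomatic (6.6.1.2) | COVID-19 (6.6.1.3) |
|---|---|---|---|---|---|
| Negative | No | Yes | Yes | Yes | No |
| Negative | Yes | Yes | Yes | No | Yes |
| Positive | No | Yes | No | No | No |
| Positive | Yes | Yes | No | No | Yes |

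The last two rows are the mismatch. They also cover anyone who cannot be classed negative: SAP 6.1 requires both a negative RT-PCR and a negative serology, so a participant with one of these missing and the other negative is in neither class and falls outside the derivation.

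The opening sentence of 6.6.1.1 is ambiguous. If its status qualifier attaches only to asymptomatic infection, the fourth row becomes an infection and only the third row is lost. The rule that follows does not allow that reading, so the section gives a programmer two rules.

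**2. Size.** Inputs from the documents: 70 per arm, 6 × 70 = 420 in Part A and 2 × 70 = 140 in Part B, 560 in all (SAP 4.1 and 4.2). Inputs assumed, because the documents give neither:

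- q, the pre-booster-positive share: 5% to 30%.
- a, the rate of post-baseline positive RT-PCR among those participants: 5% to 20%.

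Cases left out per arm = 70 × q × a.

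- Low end: 70 × 0.05 × 0.05 = 0.175, about 0.2. Over both parts, 560 × 0.05 × 0.05 = 1.4.
- High end: 70 × 0.30 × 0.20 = 4.2. Over both parts, 560 × 0.30 × 0.20 = 33.6.

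Effect on the percentage, with q = 20%, a = 10% and an assumed 20% infection rate in pre-booster negatives:

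- SAP rule on the FAS: 70 × 0.80 × 0.20 = 11.2 cases, and 11.2/70 = 16.0%.
- Endpoint as stated, on the FAS: 11.2 + 70 × 0.20 × 0.10 = 11.2 + 1.4 = 12.6 cases, and 12.6/70 = 18.0%.
- Negatives only, in numerator and denominator: 11.2/56 = 20.0%.

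The 16.0% estimates neither the stated endpoint nor the risk in baseline negatives.

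**The case against.** **Restricting to baseline negatives is legitimate, and the SAP takes precedence.** A first-infection count in negatives is a sensible estimand. But the precedence clause in SAP section 1 settles SAP against protocol. It does not settle SAP 3.1.3 and 3.2.3 against SAP 6.6.1.1. Nor does it justify the FAS denominator, which a negatives-only estimand would not use.

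**A reader might infer that every PCR-confirmed reinfection is lost from the trial.** The documents do not support that. Symptomatic cases in pre-booster positives remain in the COVID-19 summaries and are recorded as medically attended events (protocol 7.3.6 and 7.4.4). Someone with a past infection who tests negative on both baseline tests is classed negative, and a new infection in that person is counted. Protocol 3.1 also has surveillance-detected infections reported as adverse events, although the schedule of events records unsolicited events only through Day 29.

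**A reader might infer that COVID-19 cases are plainly not a subset of infections, or that an arm could report fewer infections than COVID-19 cases.** The first depends on which sentence of 6.6.1.1 governs. The second requires COVID-19 in pre-booster positives to outnumber all asymptomatic and serology-only infections in negatives. If positives have a COVID-19 risk r relative to negatives, their cases as a fraction of those in negatives are q × r/(1 − q). At an assumed q = 0.2 and r = 0.5 this is 0.1/0.8 = 12.5%. With repeated scheduled swabs and serology, a reversal is possible but unlikely.

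**A reader might want the loss as a percentage of infections.** A share of RT-PCR-confirmed cases alone would omit serology-only infections from its denominator and so overstate the effect on the infection table.

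**The analysis is descriptive.** Protocol 8.5.2 makes it exploratory and optional, and no hypothesis is tested. That stands and limits the severity. SAP 6.6 nevertheless commits to summarising these cases by arm.

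**Conclusion.** The point holds as a low-severity inconsistency inside the SAP. Under the operative rule in 6.6.1.1 and 6.6.1.2, RT-PCR-confirmed infections in participants not classed pre-booster negative are missing from the infection and asymptomatic-infection counts, and the FAS percentage is too low for the endpoint as stated. The ambiguity in 6.6.1.1 affects only whether symptomatic cases are also missing. Asymptomatic RT-PCR positives in these participants are missing on either reading.

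The documents cannot give the size. The 0.2 to 4.2 cases per arm of 70 and the shift from 16.0% to 18.0% rest wholly on the assumed shares and rates. No immunogenicity conclusion is affected.

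**What to change.** In SAP 6.6.1.1 and 6.6.1.2:

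- Apply the negative-baseline condition to the seroconversion limb only (anti-nucleocapsid negative on Day 1).
- Count a post-baseline positive RT-PCR whatever the pre-booster serostatus.
- State that participants RT-PCR positive on Day 1 are handled separately, because a later positive may be the same infection. The endpoint wording has no such provision, so it should be declared.
- Reword the opening sentence of 6.6.1.1 to agree with the rule that follows.
- Present infection, asymptomatic infection and COVID-19 overall and by pre-booster status, each with its matching denominator. The split in SAP 6.5 covers only selected immunogenicity and safety analyses, so it needs to be extended here.

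If a baseline-negative estimand is intended instead, restrict the denominator in 6.6.2 and the COVID-19 count shown with it to the same participants, align SAP 3.1.3 and 3.2.3, and list the change in SAP section 7.

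The cost is SAP wording and one extra split by a status that is already derived (SAP 6.1) and tabulated (SAP 6.2.2). No new data are needed. One small drawback is that the overall figure mixes first infections and reinfections, which is the reason for the split.
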